STUDY PROTOCOL
May 1, 2017

Project Title: Integrating Safer Conception Counseling to Transform HIV Family Planning Services

NCT03167879

Registered on clinicaltrials.gov on 5/23/17

STUDY PROTOCOL

Overview. This 3-arm, cluster RCT will compare two models for implementing a comprehensive FP program that integrates SCC within current FP services in HIV clinics—an up to 6-session, multi-component, structured SCC intervention (SCC1), and a workshop to train FP providers on use of SCC guidelines (SCC2)—versus existing FP services (usual care). Both SCC1 and SCC2 will use routine screening for fertility desires and a workshop for training FP nurses to implement SCC, but SCC1 is differentiated by its use of a structured counseling SCC protocol and manual (as opposed to the clinical acumen of the trained FP nurses), and inclusion of client outreach and ongoing supervision support. Each arm will be implemented at 2 sites (6 sites in total) and each site will enroll 65 clients (total n=390) with serodiscordant partners who have childbearing desires at recruitment. Participants will be surveyed at baseline, months 6 and 12, and post-pregnancy for those who become pregnant prior to month 12. The primary outcome is correct use of SCM or contraception (depending on desired pregnancy status following SCC consult); secondary outcomes are pregnancy status, PMTCT use (if pregnant), partner seroconversion, and condom use. A cost-effectiveness analysis will also compare the 3 arms to inform policy and practice recommendations for settings of various resource levels.

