Study Setting. The study will be conducted at 6 HIV clinics operated by The AIDS Support Organization (TASO), which are located in Masaka, Entebbe, Mbarara, Jinja, Mbale, and Rokangira. These sites are *highly comparable with regard to size of clientele, provider composition, and makeup of FP services, and are close enough to Kampala for facilitating effective coordination and oversight of the research*. TASO partnered with us to plan the proposed models for integrating SCC into its FP services, and to pilot SCC1 (see D.1). Each site resides within a hospital campus, provides HIV care to 6000-8000 index clients (65-75% female, 75-80% aged 15-49, ~70-80% on ART), with a staff of 15-20 medical providers (incl. 3-4 FP nurses), 12-15 counselors and 6-10 expert clients. Each provides reproductive health and FP services in-house, which focus on contraception and PMTCT; contraceptives provided onsite include oral pills, injectables, and condoms, while implants and tubal ligation require referral to nearby FP clinics. Other related services at TASO include assisted disclosure (including home-based couples HIV testing), and male circumcision.

Cluster RCT of two models for integrating SCC within existing FP programs vs. usual care

[figure not shown]
Each site will be randomly assigned (a blind drawing witnessed by the leadership of each clinic) to use one of the two models for integrating SCC into FP services (SCC1 or SCC2), or usual care (existing FP services).

Arm 1: Multi-component, structured intervention for integrating SCC into FP (SCC1)

Drawing on an ecological adaptation of the Information, Motivation and Behavioral skills (eIMB) model of behavior change,⁵⁷ we developed a multi-component intervention that identifies and engages HIV clients (and partners) with fertility desires into SCC to facilitate an informed decision process regarding childbearing and corresponding use of contraception or SCM (and PMTCT once pregnant) based on their desired pregnancy decision. Applied to this context,

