IMB asserts that **information** about the transmission risks of childbearing and how SCM and PMTCT limit these risks is a prerequisite but insufficient to ensure use of SCM/PMTCT or contraception, and that motivation and behavioral skills to use these methods are critical. **Motivation** is fed by beliefs that SCM and PMTCT greatly reduce transmission risks and contraception prevents unplanned pregnancy, and confidence in being able to use these methods. **Behavioral skills** such as calculating the fertile days of a woman's ovulation cycle, using a syringe to manually inseminate the woman, and negotiate condom and contraception use with one's partner, are key to SCM and contraception use. The **sociocultural context** for childbearing in PLHA affects each of the IMB components: HIV+ peers, providers, partners, family and community are sources of information (or misconceptions), attitudes, beliefs, and support (or stigmatization) for childbearing and use of contraception, SCM and PMTCT, all of which affect knowledge, motivation, and self-efficacy for use of these methods. Stigmatization of childbearing by providers,^{17,26,33} family and community²⁷ contributes to poor provider-patient communication about fertility needs and greatly impedes clients receiving needed SCC.

To address each eIMB construct, the multi-component intervention consists of: 1) training expert clients and village health team workers (VHTs) to engage in **client and community outreach and education** about the

childbearing needs of PLHA and availability of comprehensive FP services including SCC to promote SCM use and reduce childbearing stigma; 2) **provider training and supervision** to sensitize providers to childbearing needs of PLHA, reduce provider stigma of childbearing, and develop and sustain their skills and self-efficacy for providing SCC; 3) **routine screening of childbearing desires** to facilitate timely identification of clients in need of SCC or contraceptives; and 4) **structured, manualized SCC sessions** administered by FP nurses to promote informed childbearing decisions and use of SCM, PMTCT and contraception. The intervention will be incorporated into the clinic's model of care and applied to all clients, not only research participants.

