African healthcare workers, including expert clients and VHTs, are prone to use a more directive style when interacting with clients, rather than the autonomy supportive style of Motivational Interviewing (MI) that proved useful in our pilot. Research with lay HIV counselors in South Africa⁶⁰ demonstrates that they can be trained in MI skills and we have developed a training program that focuses on three core MI skills: open questions, reflective listening, and pulling for change talk. While not fully compliant MI counseling, use of these communication strategies may greatly enhance their success in encouraging clients to consider using SCM, and male partners to participate in FP. MI strategies may be particularly useful in enhancing clients' motivation and reducing levels of internal and external stigma thereby increasing the likelihood of clients: initiating childbearing discussions with providers, engaging partners in SCC, and being open to using SCM. Our intervention will incorporate routine screening for childbearing desires and train providers to ask clients about fertility intentions, but it is equally important to empower clients to assert their need for childbearing support. Half the trained expert clients and VHTs will be male to facilitate successful outreach to men. Clients who benefit from SCC and successfully use SCM to conceive will be asked to give brief waiting room testimonials about how SCM worked for them and how talking with their providers and accessing SCC helped. We will intentionally seek out men to participate in testimonials, to encourage other men to seek SCC.

(2) Provider training, fidelity monitoring and supervision

and supervision: Fig. 2 shows our plan for provider training and supervision. The first 4 hours of training uses experiential learning methods to sensitize providers to: their own attitudes and beliefs that stigmatize childbearing and impede rapport building; the risks and benefits of SCM; and the need for all providers to discuss fertility needs with clients. All providers (doctors, nurses, counselors, expert clients) are included in this portion of the training to increase their knowledge and understanding of their role in supporting clients' use of SCM and contraception, and

Figure 2: FP nurse training, supervision and fidelity monitoring by SCC arm

	Skills	Training Strategy	Hrs	Fidelity

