Routinely collected clinic data will be used to analyze FP services in the overall clinic population to examine clinic capacity and fidelity to the intervention. The triage book and childbearing screening item (in SCC1/SCC2 sites) will be used to determine: (a) # who do not want children and % receiving contraception services, and (b) # reporting childbearing desires. FP registries will indicate # new clients receiving FP services (not seen by FP in past year), and % of FP recipients using dual contraception. These will be tracked longitudinally to assess intervention effects on clinic level FP services. % of clients receiving FP referrals after triage will be compared across all 3 arms using research cohort data, since childbearing screening is not used at the usual care site.

Research Participants. The assigned FP programs at each study site will be implemented clinic-wide for all clinic clients, but the 66 study clients enrolled at each site will meet the following **eligibility criteria**:

1. Adults of reproductive age (men age 18-60; women age 18-45).
2. Considering childbearing with their spouse/partner. This will be determined via the triage screening item.
3. Reports having disclosed HIV status to partner. TASO counselors provide clients with assisted disclosure services to help them disclose to partners. Therefore, interested clients who have not yet disclosed their HIV status to their partner will be assisted to do so if they wish, after which they can be considered for enrollment.
4. Partner is HIV-negative. All couples can benefit from SCC and FP, but we focus on discordant couples due to the heightened value of SCC for reducing horizontal HIV transmission. We will use a rapid HIV test to confirm partner's status, and offer the option of a home-based test (a service offered by TASO) if necessary. Confirming the partner's status enables us to accurately assess intervention effects on seroconversion.

ART use is not an eligibility criterion, but SCC will be used to advise and support clients to start and adhere to ART before trying to conceive with SCM. TASO provides ART to all clients in serodiscordant relationships.

Note that only the HIV+ client will enroll in the study and participate in the survey research, not their partners.

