Recruitment. We will enroll 3-4 clients per month over 18 months at each site, which is feasible as >20 clients met this eligibility criteria in each recruitment month in our pilots. Recruitment will be stratified by sex to ensure a 50/50 gender balance, which will better enable us to examine intervention effects on partner seroconversion

and to gain the perspective of both male and female clients regarding fertility. We could enroll the sample more quickly, but the long enrollment period ensures we can recruit the target number of men, and enables us to have our 3 site coordinators manage three sites each (min. 1 day per week at each clinic) to limit personnel costs. Clients at the SCC1 and SCC2 sites who report at triage that they desire to have a child with a negative or unknown HIV status partner will be referred by triage to the site coordinator for screening. Screening (incl. partner HIV testing) and baseline survey will be completed prior to the initial SCC consultation. At the usual care site, the childbearing screening item will be included at triage only during the days of recruitment, which will be used to identify potential participants who will then be referred to the site coordinator for the same screening conducted at the intervention sites; the data from the screening item will not be placed in the client's chart or given to the FP nurse, as this screening is not part of usual care. Clients who decline to bring their partner in for HIV testing (but are otherwise eligible) and thus do not participate, will be asked to provide basic sociodemographic and partner characteristics in order to assess how they differ from the enrolled clients.

Data Collection

Assessment schedule: The baseline assessment will be done by the site coordinator once eligibility is confirmed, followed by assessments at months 6, 12, and post-pregnancy (if pregnancy occurs prior to month 12). To minimize attrition we will collect contact info (phone numbers and maps of homes), including contact information for family or friends who have frequent contact with the client. Clinic staff will also be able to help us track clients that we have difficulty reaching. In our current study we achieved 94% retention at Month 12.

Participant Compensation: Participants will receive 20,000 Ush (~\$6 USD) at each assessment.

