Data analysis: Our primary analysis will be to compare the combined intervention arms (SCC1 & SCC2) against the usual care control to assess the effects of integrating SCC into FP services, and then compare the outcomes between the two intervention arms to determine whether the more intensive SCC1 shows a larger effect than the less intensive SCC2. The primary outcome-- correct use of contraception/SCM (depending on pregnancy intention)-- will be represented as a binary variable as defined in D.2.3.5, but we will also explore a categorical or continuous outcome derived from frequency of correct use throughout the study. Secondary outcomes to be investigated are pregnancy status, PMTCT use, consistent condom use, and seroconversion of partner. We will use an intent-to-treat approach in the primary analyses; secondary analyses will use only study completers. Participants remain in the study and analysis regardless if their relationship status changes during the study. Attrition weights will be used to account for dropouts, and analyses will incorporate design effects from this weighting in the calculation of standard errors and tests of significance. We will account for clustering, and with only 9 clusters/clinics we will conduct individual level analysis. Regression methods can directly model correlations among units in a cluster (random effects or multilevel models) or more simply adjust standard errors for clustering (GEE, robust standard errors), but these approaches are not reliable with so few

clusters,⁷⁵ so we'll use standard regression methods, but rather than attempt to estimate ICC directly, we will explore the sensitivity of significance levels using a range of plausible ICCs values for the outcomes.

Aim 1: Assess intervention effect on contraception/SCM use: *Hypothesis: Both SCC1 and SCC2 will be superior to usual care, and SCC1 will be superior to SCC2 regarding the primary outcomes.* We'll use logistic regression to compare rates of contraception or SCM use (depending on pregnancy intention) in the SCC1 and SCC2 interventions compared to the control condition, and investigate differences between SCC1 and SCC2 in a separate regression. The models will include covariates to adjust for baseline variables (e.g., childbearing stigma, age, sex) that may differ at baseline and to increase precision of the estimates.

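### Does adjusting for baseline childbearing stigma strip out part of the SCC1 effect?

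*Combined protocol and SAP*

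**What the plan says.** The Data Analysis Plan, Aim 1, compares rates of correct contraception or SCM use by logistic regression and takes SCC1 against SCC2 in a separate model. The models are to "adjust for baseline variables (e.g., childbearing stigma, age, sex) that may differ at baseline and to increase precision of the estimates". Aim 2 uses the same strategy for the secondary outcomes. The table of mediators and moderators under Measures lists three childbearing-stigma scales: internalised, perceived provider and perceived community. Aim 1 does not say which one it means.

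On timing and exposure:

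- Allocation is by clinic: "Each site will be randomly assigned".
- SCC1 differs from SCC2 partly by its "inclusion of client outreach and ongoing supervision support" (Overview).
- The first SCC1 component is outreach on "comprehensive FP services including SCC to promote SCM use and reduce childbearing stigma". On the counselling style used there, the plan says "MI strategies may be particularly useful in enhancing" motivation and in lowering stigma.
- Under Research Participants: "The assigned FP programs at each study site will be implemented clinic-wide for all clinic clients".
- Under Recruitment: "We will enroll 3-4 clients per month over 18 months at each site", and the "baseline survey will be completed prior to the initial SCC consultation".

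**The concern.** In an individually randomised trial, a baseline covariate precedes allocation and cannot carry a treatment effect. Here the label is weaker. Stigma is measured when a client enrols, which may be many months after the clinic was allocated. Baseline must come before the client's own SCC consult, but nothing places it before the waiting-room and village outreach. An SCC1 client recruited late in the 18 months could have heard that outreach several times.

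If outreach lowered stigma and lower stigma raises correct use, stigma lies on the causal path. Adjusting for it then removes that part of the total SCC1 effect. The loss would fall mostly on SCC1 versus SCC2, the contrast meant to show whether the costlier package is worth having, and would be diluted in the pooled comparison with usual care. Because the covariates are given only as examples, the choice also appears open until results are known.

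**Working it through.** The plan gives no figure on this point, so there is none to reproduce. Its 7 to 8 point detectable difference for SCC1 versus SCC2 is not a usable yardstick. With its own ICC and attrition, and two-sided 5% assumed, power for 7.5 points above 19.5% is only about 19%. That is a separate matter.

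**Inputs from the documents.** 65 clients per site, two sites per arm, 10% attrition, ICC 0.01, usual-care rate 15%, pooled difference 4.5 points (so 19.5%).

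**Assumptions, not in the documents.** Outreach lowers stigma by 0.1 to 0.3 SD before baseline, in SCC1 only. The outcome slope is 0.3 to 0.5 log-odds per SD. The SCC2 rate is 15% or 19.5%, with SCC1 7 to 8 points higher.

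**Standard error, SCC1 versus SCC2.**
- Analysed per arm: 130 × 0.9 = 117, or 58.5 per site. Design effect: 1 + 57.5 × 0.01 = 1.575.
- SE = √[1.575 × (1/(117·p₁q₁) + 1/(117·p₂q₂))].
- 15% v 22%: √[1.575 × (0.0670 + 0.0498)] = 0.429.
- 19.5% v 27.5%: √[1.575 × (0.0544 + 0.0429)] = 0.392.

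**Loss from adjusting, if the shift is real.**
- Every SCC1 participant exposed: 0.1 × 0.3 = 0.03 to 0.3 × 0.5 = 0.15 log-odds. In SE units, 0.03/0.429 = 0.07 to 0.15/0.392 = 0.38.
- In points: taking 0.03 off the logit of 22% gives 21.5% (0.5 points lost); taking 0.15 off the logit of 27.5% gives 24.6% (2.9 points lost).
- Half exposed: 0.015/0.429 = 0.03 to 0.075/0.392 = 0.19 SE. None exposed: zero.
- Pooled contrast (117 v 234, 15% v 19.5%, SE 0.385): SCC1 is half the combined arm, so 0.015/0.385 = 0.04 to 0.075/0.385 = 0.19 SE.
- A wider assumed grid (drop 0.1 to 0.5 SD, odds ratio 0.8 to 0.5 per SD) gives 0.4 to 6.1 points for SCC1 versus SCC2 and 0.2 to 2.7 pooled. Nothing in the documents supports its upper corner.

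**Harm from not adjusting.**
- The SD of a purely chance SCC1–SCC2 stigma difference at baseline is √[2(1 + 64·ICC)/130]. For assumed stigma ICCs of 0.01, 0.02 and 0.05 this is 0.16, 0.19 and 0.25 SD, much the size of the assumed shift.
- Simulation with a 0.3 SD difference, slope 0.5 and a set effect of 0.469 log-odds (15% v 22%):

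| Source of the stigma difference | Unadjusted | Adjusted |
|---|---|---|
| Outreach lowers stigma in SCC1 | 0.459 | 0.324 |
| Selection raises stigma in SCC1 | 0.310 | 0.471 |
| No difference | 0.443 | 0.461 |

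In the first row adjustment falls short by 0.469 − 0.324 = 0.145. In the second, omission falls short by 0.469 − 0.310 = 0.159. The errors are near mirror images. The small gap in the third row is the usual change in an odds ratio on adjustment; in a separate population-level calculation with no shift, the risk differences were identical.

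**Precision.** Variance explained is about slope² × p(1 − p): 0.09 × 0.1275 = 1.1% to 0.25 × 0.1716 = 4.3%. Precision does not decide the matter either way.

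**The case for a change.** The best case for a change is that the plan itself lists stigma among possible mediators, names its reduction as an aim of SCC1, and then proposes to condition on it in the model for the total effect. SCC1 versus SCC2 is a stated hypothesis, and outreach is part of what it tests. Keeping only covariates that outreach cannot touch, and showing the stigma-adjusted result beside them, would be cheap and would take the choice away from whoever sees the results first.

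Part of this stands. The timing gap is real, the list is open and the scale is unnamed. Perceived provider stigma could move at SCC2 sites too, since the nurse training there covers the history of stigma.

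The step to a different primary model does not stand:

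- Selection is at least as plausible as contamination. Intervention sites screen for childbearing desire routinely, usual-care sites only on recruitment days. Outreach also urges clients to voice fertility desires, so it may change who enrols. Adjusting for variables that may differ is a sound response.
- Full exposure is a ceiling. Reading the four expert clients and four village workers as a per-site number, eight people serve 6000 to 8000 clients, one per 750 to 1000. Group talks stretch that, but not to everyone.
- Age and sex alone are thin protection, because recruitment already balances sex by design.
- Estimates with and without stigma cannot tell an outreach effect from imbalance. If they disagreed, the only advice would be caution.

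**Conclusion.** No change is needed. The concern identifies a possible bias, not one the documents show. Under the assumed 0.1 to 0.3 SD shift and 0.3 to 0.5 slope, adjustment costs at most 0.15 log-odds (2.9 points, 0.38 SE) in SCC1 versus SCC2 and 0.19 SE in the pooled comparison, and nothing if stigma has not moved. A loss at the top of that range could tip a borderline result. Omitting stigma could do the same under selection of equal size, and chance differences between two-site arms are as large as the assumed shift. Reasonable statisticians would differ on which model should lead, and the plan's choice is defensible. Closing the list and naming the scale are ordinary details for analysts to settle before the data are examined; their absence makes no stated result wrong. All of this rests on assumed values for the shift, slope, exposure and stigma ICC, none of which the documents supply.

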Measures. Assessments will include measures of the primary and secondary outcomes and variables that map to our eIMB conceptual framework for understanding use of SCM and contraception, as listed below. Survey measures have been translated into Luganda in our prior research. The survey will be interviewer-administered using computer-assisted software, and administration time is 45-60 minutes.

Primary outcome: Correct use of contraception or SCM over the past 6 months, depending on pregnancy intentions; a single binary indicator will be created for use as the primary outcome, while continuous and categorical measures of frequency and duration of use will be used in secondary analyses. Correct use of contraception is defined as always using both condoms and another modern contraceptive (e.g., oral pills, DEPO injection, IUD implant) (i.e., dual contraception) over the past 6 months (since last survey), and will be ascertained via self-report and chart review (provision of non-condom contraceptive). Male participants will be asked to consent (it won't be required) to the coordinator calling their partner on the phone to assess use of non-condom contraceptives; these data will be kept confidential from the male. This definition is consistent with FP policy and practice in Uganda,⁶⁶ as condoms are important for HIV prevention, but used too inconsistently to prevent pregnancy, hence the need for an added contraceptive. If a participant becomes single or abstinent during the course of the study, avoiding pregnancy and use of contraception will be considered the desired behavior. The primary outcome will define whether SCM or contraception use was consistent (and changed to correspond with changes in pregnancy intentions) with pregnancy intentions over the entire study period.

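### The Aim 1 model does not fix its covariates in advance and does not name baseline contraceptive and SCM behaviour among them, although the baseline survey appears to collect it

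*Combined protocol and SAP*

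**What the plan says.** Data Analysis Plan, Aim 1, sets out the model: "We'll use logistic regression to compare rates of contraception or SCM use (depending on pregnancy intention"). SCC1 and SCC2 are compared in a separate regression. Covariates are given only as examples (childbearing stigma, age and sex), with two reasons attached: they are ones "that may differ at baseline and to increase precision of the estimates". No closed list or selection rule for Aim 1 appears elsewhere, and Aim 2 adopts the same strategy.

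On what is available at baseline:

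- Measures: "Assessments will include measures of the primary and secondary outcomes". No assessment is excepted.
- Data Collection, assessment schedule: "The baseline assessment will be done by the site coordinator once eligibility is confirmed, followed by assessments at months 6, 12".
- Recruitment: "Screening (incl. partner HIV testing) and baseline survey will be completed prior to the initial SCC consultation".
- The correct-contraception definition covers use "over the past 6 months (since last survey"). No separate baseline version is defined.

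The Overview has two sites per arm, six in all, with 65 clients each. Study Setting describes allocation as a blind drawing and mentions no stratification, matching or constraint. It calls the sites highly comparable in clientele size, provider composition and family-planning services, but is silent on clients' prior behaviour.

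**The concern.** Whether a covariate happens to differ between arms is a poor reason to adjust for it. What matters is whether it predicts the outcome, and the list should be settled before outcome data are seen. Earlier contraceptive, condom and SCM use is an obvious candidate predictor of the same behaviour at month 12, yet the confirmatory model does not commit to it. Aim 3, by contrast, plans to look for baseline correlates of the primary outcome and to study change in it, which suggests that a baseline measurement is expected.

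Two things are at stake. An open list lets covariates be chosen after the results are known. And with so few clinics drawn without restriction, the arms may start apart in prior behaviour by as much as the effect the trial is meant to detect. To the extent that behaviour persists, this biases the realised comparison.

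**Working it through.** **Inputs from the protocol.** Six clinics, 65 per clinic: 130 usual care and 260 combined (Overview). Month-12 usual-care rate 15%, ICC 0.01, attrition 10%, target difference 4.5 points, more than 80% power, two-tailed (Power analysis). **Assumed:** alpha 0.05; baseline rate of correct use 15% or 3%; baseline to month-12 correlation r. The documents give none of these. The Data analysis text refers to 9 clinics; six is used here, and the two counts need reconciling.

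**1. The plan's power figure.** Retained per clinic: 65 × 0.9 = 58.5. Design effect: 1 + 57.5 × 0.01 = 1.575. Effective numbers: 117/1.575 = 74.3 and 234/1.575 = 148.6. For 15% versus 19.5%, the pooled rate is 18%.

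- Null SE = √[0.18 × 0.82 × (1/74.3 + 1/148.6)] = 0.0546
- Alternative SE = √[0.1275/74.3 + 0.156975/148.6] = 0.0527
- z = (0.045 − 1.96 × 0.0546)/0.0527 = −1.18, so power is about 12%.

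The stated figure of more than 80% is not reproduced. That is a separate issue, but it shows how little precision there is to spare.

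**2. Chance baseline imbalance.** SD = √[p(1−p) × (1 + 64 × ICC) × (1/n₁ + 1/n₂)].

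| Assumed baseline rate | Contrast | SD (points) | Chance of exceeding 4.5 points |
|---|---|---|---|
| 15% | usual care vs combined | √[0.1275 × 1.64 × (1/130 + 1/260)] = 4.9 | 36% |
| 15% | SCC1 vs SCC2 | √[0.1275 × 1.64 × 2/130] = 5.7 | 43% |
| 3% | usual care vs combined | √[0.0291 × 1.64 × (1/130 + 1/260)] = 2.35 | 5.5% |

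**3. Precision gain.** As an approximation, residual variance is multiplied by 1 − r². With 390 × 0.9 = 351 analysed clients, the equivalent extra number is 351 × [1/(1 − r²) − 1].

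| r | Variance reduction | Equivalent extra clients |
|---|---|---|
| 0.2 | 4% | 15 |
| 0.3 | 9% | 35 |
| 0.5 | 25% | 117 |

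This is a linear-scale formula, so it applies to a risk difference and not to a log odds ratio.

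**4. Simulation of six clinics of 58, logistic regression with and without the baseline outcome.** At a 15% baseline rate, the variance of the risk difference fell by about 4%, 10% and 28% at binary correlations of 0.15, 0.28 and 0.44. At a 3% rate it fell by about 1%, 6% and 14% under the same three settings. A second set, assuming 15% versus 27% at month 12, gave about 12-36% at correlations of 0.16-0.43, with power rising from about 69% to 71-78%. The simulated gain is sensitive to how far clinic differences persist from baseline to month 12, which the documents do not inform, so these figures are only illustrative.

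**5. The odds-ratio scale.** In the second set, the SE of the log odds ratio went from 0.31 to 0.31-0.35. In an unclustered simulation of 117 versus 234 clients (15% versus 27%), it rose from 0.302 to 0.317 at a correlation of 0.27, and from 0.303 to 0.357 at 0.48. The mean log odds ratio moved from 0.75 to 0.82 and from 0.76 to 1.00. Power can rise because the estimate moves further than its SE, but the interval does not narrow.

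**6. What adjustment leaves unrepaired.** Type I error of the standard logistic model was about 10-12% without the baseline outcome and 9-12% with it. Power at 4.5 points moves from 12.0% to 12.8% at r = 0.3 and 14.8% at r = 0.5. Reaching 80% would need r of about 0.95.

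**The case against.** The list is open, precision is one of the two stated reasons, and no baseline testing or data-driven selection is described for Aim 1. All of that is correct. A reader might infer that the plan excludes baseline behaviour, or chooses covariates solely on imbalance; the text supports neither. What stands is that the plan neither names nor prespecifies it.

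The baseline value may also be poorly defined or weakly predictive. The outcome depends on pregnancy intention after the consult, whereas everyone enters considering childbearing and about half are expected to choose contraception later. That baseline use is measured is itself an inference from the Measures section. For male participants, partner-reported contraceptive data need optional consent, so gaps are possible. These points limit the gain and argue for adjusting for components rather than a baseline composite. They do not argue against prespecification.

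A further tempting inference is that a clinic difference passes straight into the arm effect. If one clinic starts 10 points lower, a two-clinic arm starts 5 points lower, but one of the four combined clinics shifts that mean by only 2.5. Under the plan's ICC, the true between-clinic SD is √(0.01 × 0.1275) = 3.6 points, so a true 10-point deficit is 10/3.6, or about 2.8 SD. Imbalance carries over only as far as behaviour persists: with r of 0.2-0.5 and similar rates, adjustment for a 5-point gap removes about r × 5 = 1.0-2.5 points.

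**Conclusion.** The point holds as a gap in prespecification with a cheap and better alternative. The Aim 1 covariates are not fixed, possible baseline difference is offered as a reason for including them, and baseline behaviour is not named although it appears to be collected before the first consult. The chance baseline difference between usual care and the combined arms has an SD of about 4.9 points if the baseline rate is 15%, slightly above the 4.5-point target, and about 2.35 points if it is 3%. The variance gain is about 4-25% for r between 0.2 and 0.5, and small if baseline use is rare or weakly predictive. Both the rate and r are assumptions.

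Two stronger conclusions should not be drawn. Adjustment does not narrow the odds-ratio interval, so its benefit has to be read on the risk-difference scale or in power. Nor does it rescue the design: with six clinics it protects only partially against imbalance, and the clustering and stated-power problems remain.

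**What to change.** Replace the covariate sentence in Aim 1 with a closed list that applies whatever differences are observed:

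- sex (the recruitment stratum);
- age;
- baseline past-6-month consistent condom use, modern contraceptive use and SCM use.

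Define these baseline components explicitly, since no earlier survey exists to anchor the recall period. State a rule for merging or dropping a component that is too sparse, and how missing values are handled. Remove possible baseline difference as a reason for selection. Use the same list for the SCC1 versus SCC2 regression.

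Report the effect as a covariate-standardised risk difference from the logistic model, with the unadjusted risk difference beside it, and apply the plan's range-of-ICC sensitivity to both. Adjusted and unadjusted odds ratios should not be compared as a diagnostic: the odds ratio is non-collapsible, so they differ even when nothing is wrong.

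The cost is a few sentences of protocol text and no new data collection. The downsides are small: some components may be sparse or incomplete, and adjustment would be slightly conservative if clinic outreach had already changed behaviour before enrolment.
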